### **7.2.2. Assessment of Severity**

AE severity should be recorded and graded according to the modified GSI Grading Scale for Severity of Adverse Events and Laboratory Abnormalities (see [Appendix 4](#) for more information). For AEs associated with laboratory abnormalities, the event should be graded on the basis of the clinical severity in the context of the underlying conditions; this may or may not be in agreement with the grading of the laboratory abnormality.

The distinction between the seriousness and the severity of an adverse event should be noted.

Severe is a measure of intensity; thus, a severe reaction is not necessarily a serious reaction. For example, a headache may be severe in intensity, but would not be classified as serious unless it met one of the criteria for serious events.

For AEs associated with laboratory abnormalities, the event should be graded on the basis of the clinical severity in the context of the underlying conditions; this may or may not be in agreement with the grading of the laboratory abnormality.

### **7.3. Investigator Requirements and Instructions for Reporting Adverse Events and Serious Adverse Events to Gilead**

#### **7.3.1. Requirements for collection prior to study drug initiation:**

After informed consent, but prior to initiation of study medication, the following types of events should be reported on the case report form (CRF/eCRF): all SAEs and AE related to protocol-mandated procedures.

##### **7.3.1.1. Adverse Events**

Following initiation of study medication, collect all AEs, regardless of cause or relationship, until 30 days after last administration of study drug must be reported to the CRF/eCRF database as instructed.

All AEs should be followed up until resolution or until the AE is stable, if possible. Gilead Sciences may request that certain AEs be followed beyond the protocol defined follow up period.

##### **7.3.1.2. Serious Adverse Events**

All SAEs, regardless of cause or relationship, that occurs after the subject first consents to participate in the study (ie, signing the informed consent) and throughout the duration of the study, including the protocol-required post treatment follow-up period, must be reported to the CRF/eCRF database and Gilead DSPH as instructed. This also includes any SAEs resulting from protocol-associated procedures performed after informed consent is signed.

Any SAEs and deaths that occur after the post treatment follow-up visit but within 30 days of the last dose of study drug, regardless of causality, should also be reported.

Investigators are not obligated to actively seek SAEs after the protocol defined follow up period, however, if the investigator learns of any SAEs that occur after study participation has concluded and the event is deemed relevant to the use of study drug, he/she should promptly document and report the event to Gilead DSPH.

- All AEs and SAEs will be recorded in the CRF/eCRF database within the timelines outlined in the CRF/eCRF completion guideline.

#### 7.3.1.3. Electronic Serious Adverse Event (eSAE) Reporting Process

- Site personnel record all SAE data in the eCRF database and from there transmit the SAE information to Gilead DSPH within 24 hours of the investigator's knowledge of the event. Detailed instructions can be found in the eCRF completion guidelines.
- If for any reason it is not possible to record the SAE information electronically, ie, the eCRF database is not functioning, record the SAE on the paper SAE reporting form and submit within 24 hours as described below.

Gilead DSPH:	Fax: E-mail:	PPD PPD
---------------------	-----------------	------------

- As soon as it is possible to do so, any SAE reported via paper must be transcribed into the eCRF Database according to instructions in the eCRF completion guidelines.
- If an SAE has been reported via a paper form because the eCRF database has been locked, no further action is necessary.
- For fatal or life-threatening events, copies of hospital case reports, autopsy reports, and other documents are also to be submitted by e-mail or fax when requested and applicable. Transmission of such documents should occur without personal subject identification, maintaining the traceability of a document to the subject identifiers.
- Additional information may be requested to ensure the timely completion of accurate safety reports.
- Any medications necessary for treatment of the SAE must be recorded onto the concomitant medication section of the subject's CRF/eCRF and the event description section of the SAE form.

#### 7.4. Gilead Reporting Requirements

Depending on relevant local legislation or regulations, including the applicable US FDA Code of Federal Regulations, the EU Clinical Trials Directive (2001/20/EC) and relevant updates, and other country-specific legislation or regulations, Gilead may be required to expedite to

worldwide regulatory agencies reports of SAEs, serious adverse drug reactions (SADRs), or suspected unexpected serious adverse reactions (SUSARs). In accordance with the EU Clinical Trials Directive (2001/20/EC), Gilead or a specified designee will notify worldwide regulatory agencies and the relevant IEC in concerned Member States of applicable SUSARs as outlined in current regulations.

Assessment of expectedness for SAEs will be determined by Gilead using reference safety information specified in the IB or relevant local label as applicable.

All investigators will receive a safety letter notifying them of relevant SUSAR reports associated with any study drug. The investigator should notify the IRB or IEC of SUSAR reports as soon as is practical, where this is required by local regulatory agencies, and in accordance with the local institutional policy.

#### **7.5. Clinical Laboratory Abnormalities and Other Abnormal Assessments as Adverse Events or Serious Adverse Events**

Laboratory abnormalities are usually not recorded as AEs or SAEs. However, laboratory abnormalities (eg, clinical chemistry, hematology, and urinalysis) independent of the underlying medical condition that require medical or surgical intervention or lead to investigational medicinal product interruption or discontinuation must be recorded as an AE, as well as an SAE, if applicable. In addition, laboratory or other abnormal assessments (eg, ECG, X-rays, vital signs) that are associated with signs and/or symptoms must be recorded as an AE or SAE if they meet the definition of an AE (or SAE) as described in Sections 7.1.1 and 7.1.2. If the laboratory abnormality is part of a syndrome, record the syndrome or diagnosis (ie, anemia) not the laboratory result (ie, decreased hemoglobin).

Severity should be recorded and graded according to the Gilead Grading Scale for Severity of Adverse Events and Laboratory Abnormalities as described in [Appendix 4](#). The GSI Grading Scale for Severity of Adverse Events and Laboratory Abnormalities has been modified to be more appropriate for healthy volunteers and patients with inflammatory diseases (eg, rheumatoid arthritis, asthma, psoriasis). For AEs associated with laboratory abnormalities, the event should be graded on the basis of the clinical severity in the context of the underlying conditions; this may or may not be in agreement with the grading of the laboratory abnormality.

#### **7.6. Toxicity Management**

Treatment-emergent toxicities will be noted by the investigator and brought to the attention of the Gilead medical monitor (MM), who will have a discussion with the investigator and decide the appropriate course of action. Whether or not considered treatment-related, all subjects experiencing AEs must be monitored periodically until symptoms subside, any abnormal Grade 3 or 4 clinically significant laboratory abnormalities should be managed as outlined in [Appendix 2](#).

Any questions regarding toxicity management should be directed to the Gilead MM.

## **7.7. Study Specific Stopping Criteria**

Study drug dosing of a cohort will be suspended and, based on full review of the clinical data by the MM and in discussion with the investigator, may be halted when:

- 2 healthy control subjects dosed with GS-9674 within a cohort experience elevations in liver function tests of ALT and/or AST > 5 x the upper limits of normal (ULN); or ALT > 3 x ULN and total bilirubin > 2 x ULN, confirmed by immediate repeat testing.
- 2 hepatic impairment subjects dosed with GS-9674 within a cohort experience elevation of baseline liver function tests of ALT and/or AST > 3 x baseline; or ALT > 2 x baseline and total bilirubin > 2 x baseline.
- 1 subject experiences a SAE possibly related to the study drug
- The sponsor unilaterally requests it.

Decisions to reinstate the study will be made in consultation with the sponsor and pending a safety review.

## **7.8. Special Situations Reports**

### **7.8.1. Definitions of Special Situations**

Special situation reports include all reports of medication error, abuse, misuse, overdose, reports of AEs associated with product complaints, occupational exposure with an AE, pregnancy reports regardless of an associated AE, and an AE in an infant following exposure from breastfeeding.

Medication error is any unintentional error in the prescribing, dispensing, or administration of a medicinal product while in the control of the health care provider, subject, or consumer.

Abuse is defined as persistent or sporadic intentional excessive use of a medicinal product by a subject.

Misuse is defined as any intentional and inappropriate use of a medicinal product that is not in accordance with the protocol instructions or the local prescribing information.

An overdose is defined as an accidental or intentional administration of a quantity of a medicinal product given per administration or cumulatively that is above the maximum recommended dose as per protocol or in the product labeling (as it applies to the daily dose of the subject in question). In cases of a discrepancy in drug accountability, overdose will be established only when it is clear that the subject has taken the excess dose(s). Overdose cannot be established when the subject cannot account for the discrepancy except in cases in which the investigator has reason to suspect that the subject has taken the additional dose(s).

Product complaint is defined as complaints arising from potential deviations in the manufacture, packaging, or distribution of the medicinal product.

## **7.8.2. Instructions for Reporting Special Situations**

### **7.8.2.1. Instructions for Reporting Pregnancies**

The investigator should report pregnancies in female study subjects that are identified after initiation of study drug and throughout the study, including the poststudy drug follow-up period, to Gilead DSPH using the pregnancy report form within 24 hours of becoming aware of the pregnancy.

Refer to Section 7.3 and the eCRF completion guidelines for full instructions on the mechanism of pregnancy reporting.

The pregnancy itself is not considered an AE nor is an induced elective abortion to terminate a pregnancy without medical reasons.

Any premature termination of pregnancy (eg, a spontaneous abortion, an induced therapeutic abortion due to complications or other medical reasons) must be reported within 24 hours as an SAE. The underlying medical reason for this procedure should be recorded as the AE term.

A spontaneous abortion is always considered to be an SAE and will be reported as described in Section 7.3. Furthermore, any SAE occurring as an adverse pregnancy outcome post study must be reported to Gilead DSPH. The subject should receive appropriate monitoring and care until the conclusion of the pregnancy. The outcome should be reported to Gilead DSPH using the pregnancy outcome report form. If the end of the pregnancy occurs after the study has been completed, the outcome should be reported directly to Gilead DSPH by emailing **PPD** or faxing **PPD**

Pregnancies of female partners of male study subjects exposed to Gilead or other study drugs must also be reported and relevant information should be submitted to Gilead DSPH using the pregnancy and pregnancy outcome forms within 24 hours. Monitoring of the pregnancy should continue until its conclusion. If the end of the pregnancy occurs after the study has been completed, the outcome should be reported directly to Gilead DSPH by faxing **PPD** or emailing **PPD**

Refer to [Appendix 3](#), Pregnancy Precautions, Definition for Female of Childbearing Potential, and Contraceptive Requirements.

### **7.8.2.2. Reporting Other Special Situations**

All special situations reports (SSRs) will be recorded in the CRF/eCRF database within the timelines outlined in the CRF/eCRF completion guideline.

Electronic Special Situations Report (eSSR) Reporting Process

- Site personnel record all SSR data in the eCRF database and from there transmit the SSR information to Gilead DSPH within 24 hours of the investigator’s knowledge of the event. Detailed instructions can be found in the eCRF completion guidelines.
- If for any reason it is not possible to record the SSR information electronically, i.e., the eCRF database is not functioning, record the SSR on the paper serious adverse event reporting form and submit within 24 hours to:

Gilead DSPH:	E-mail: Fax:	PPD PPD
---------------------	-----------------	------------

As soon as it is possible to do so, any SSR reported via paper must be transcribed into the eCRF Database according to instructions in the eCRF completion guidelines.

If an SSR has been reported via a paper form because the eCRF database has been locked, no further action is necessary.

Special situations involving non-Gilead concomitant medications does not need to be reported on the special situations report form; however, for special situations that result in AEs due to a non-Gilead concomitant medication, the AE should be reported on the AE form.

Any inappropriate use of concomitant medications prohibited by this protocol should not be reported as “misuse” but may be more appropriately documented as a protocol deviation.

Refer to Section 7.3 and the CRF/eCRF completion guidelines for full instructions on the mechanism of special situations reporting.

All clinical sequelae in relation to these special situation reports will be reported as AEs or SAEs at the same time using the AE CRF/eCRF and/or the SAE report form. Details of the symptoms and signs, clinical management, and outcome will be reported, when available.

## **8. STATISTICAL CONSIDERATIONS**

### **8.1. Analysis Objectives and Endpoints**

#### **8.1.1. Analysis Objectives**

The primary objective of this study is as follows:

- To evaluate the single-dose PK of GS-9674 in subjects with normal hepatic function, or mild, moderate and severe hepatic impairment

The secondary objectives of this study are as follows:

- To evaluate the safety and tolerability of GS-9674 single dose administration in subjects with normal hepatic function, or mild, moderate, and severe hepatic impairment
- To evaluate FXR activation by GS-9674 as measured by PD markers in subjects with normal hepatic function, or mild, moderate and severe hepatic impairment

#### **8.1.2. Primary Endpoint**

The primary endpoints are single dose plasma PK parameters of GS-9674  $AUC_{last}$ ,  $AUC_{inf}$ , and  $C_{max}$ . Additional PK parameters calculated include:  $\%AUC_{exp}$ ,  $C_{last}$ ,  $T_{max}$ ,  $T_{last}$ ,  $\lambda_z$ ,  $CL/F$ ,  $V_z/F$ , and  $T_{1/2}$  as appropriate.

#### **8.1.3. Secondary Endpoint**

The secondary endpoints are the incidences of AEs and laboratory abnormalities, physical examinations, vital signs, ECGs, and PD markers including but not limited to FGF19 and C4.

### **8.2. Analysis Conventions**

#### **8.2.1. Analysis Sets**

##### **8.2.1.1. Safety**

The Safety Analysis Set will include all enrolled subjects who received at least 1 dose of study drug. Subjects who received treatment other than that to which they were assigned will be analyzed according to the treatment received.

##### **8.2.1.2. Pharmacokinetics**

The PK Analysis Set for GS-9674 will include all enrolled subjects who received at least 1 dose of GS-9674 and had at least 1 non-missing PK concentration data reported by PK lab for each respective analyte.

### 8.2.1.3. Pharmacodynamics

Each PD analysis set will include all enrolled subjects who received at least 1 dose of study drug and have at least 1 non-missing PD value for each respective PD parameter.

## 8.3. Data Handling Conventions

For summary statistics, PK concentration values below the limit of quantitation (BLQ) will be treated as zero at predose and one-half of the lower limit of quantitation (LLOQ) for postdose time points.

Laboratory data that are continuous in nature but are less than the lower limit of quantitation or above the upper limit of quantitation will be imputed to the value of the lower or upper limit minus or plus one significant digit, respectively (eg, if the result of a continuous laboratory test is < 20, a value of 19 will be assigned; if the result of a continuous laboratory test is < 20.0, a value of 19.9 will be assigned).

Missing data can have an impact upon the interpretation of the trial data. As this study is of short duration, it is anticipated that missing data will be minimal. In general, values for missing data will not be imputed. However, a missing pretreatment laboratory result would be treated as normal (ie., no toxicity grade) for the laboratory abnormality summary.

## 8.4. Demographic Data and Baseline Characteristics

Demographic and baseline measurements will be summarized and descriptive statistics will be provided.

## 8.5. Interim Analysis

There is no formal interim analysis in this study.

## 8.6. Safety Analysis

All safety data collected on or after the date that study drug was first administered up to the date of last dose of study drug plus 30 days will be summarized by hepatic function group (according to the study drug received) using safety analysis set.

### 8.6.1. Extent of Exposure

A subject's extent of exposure to study drug data will be generated from the study drug administration page in eCRF. Exposure data will be listed.

### **8.6.2. Adverse Events**

Clinical and laboratory AEs will be coded using the Medical Dictionary for Regulatory Activities (MedDRA). System Organ Class (SOC), High-Level Group Term (HLGT), High-Level Term (HLT), Preferred Term (PT), and Lower-Level Term (LLT) will be attached to the clinical database.

Adverse event data will be listed by subject. Treatment-emergent AE (TEAE), Serious TEAE, and TEAE leading to discontinuation of treatment will be summarized by hepatic function group, system organ class, and preferred term using the current version the Medical Dictionary for Regulatory Activities (MedDRA).

### **8.6.3. Laboratory Evaluations**

Listings of individual subject laboratory results will be provided. Laboratory results and change from predose values for selected lab tests will be summarized by hepatic function group at scheduled visits. The incidence of treatment-emergent graded laboratory abnormalities will be summarized by hepatic function group.

### **8.6.4. Other Safety Evaluations**

Vital signs and ECG data will be listed by subject and visit, and summarized by hepatic function group and visit.

### **8.7. Pharmacokinetic Analysis**

Plasma concentrations and PK parameters will be listed and summarized for GS-9674 using descriptive statistics by hepatic function group (normal and mildly impaired, moderately impaired, or severely impaired) within cohort.

In addition, an ANOVA model with hepatic function group as a fixed effect will be fitted to the natural logarithmic transformation of PK parameters ( $AUC_{last}$ ,  $AUC_{inf}$ , and  $C_{max}$ ) for GS-9674 for each cohort. Two-sided 90% CIs will be calculated for the ratios of GLSM of PK parameters for GS-9674 between mild, moderate or severe hepatic impairment group and the control (normal hepatic function) group. If the upper bound of the two-sided 90% CIs of the GLSM ratio for  $AUC_{last}$ ,  $AUC_{inf}$ , and  $C_{max}$  is smaller than 2.0, the null hypothesis that subjects with mild, moderate or severe hepatic impairment exhibit average PK parameter increases of at least 100% for GS-9674 compared with subjects with normal liver function will be rejected.

GS-9674 percent protein binding will be summarized by hepatic function group and data for individual subjects will be presented in a listing. Unbound PK parameters such as  $CL_u/F$ , and  $V_{Z_u}/F$  will be calculated and summarized by hepatic function group. Relationships between measures of hepatic function (ie, CPT score, serum albumin, total bilirubin, prothrombin time and INR) and GS-9674 PK parameters will be evaluated.

### **8.8. Pharmacodynamics Analysis**

Pharmacodynamics data will be listed and summarized using descriptive statistics by hepatic function within and across cohorts.

### **8.9. Pharmacokinetics and Pharmacodynamics Analysis**

The PK/PD relationship may be explored using a graphic approach and correlation coefficients as appropriate.

### **8.10. Sample Size**

For each cohort, with 16 (8 per group) evaluable subjects, the estimated upper limit of one-sided 95% CI of the GLSM ratio of (mild, moderate or severe) hepatic impaired group vs control (normal hepatic function), with regards to  $AUC_{last}$ ,  $AUC_{inf}$ , and  $C_{max}$ , would be less than 200% with  $\geq 88\%$  probability, if the estimated GLSM ratio were 1.0. This is assuming a SD of no more than 0.463 on a natural logarithm scale, supported by previous Gilead study GS-US-402-1851. With 25% overage, a total sample size of 60 subjects (10 per group, 20 per cohort) will be required.

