(mild, moderate or severe) hepatic impaired group vs control (normal hepatic function), with regards to  $AUC_{last}$ ,  $AUC_{inf}$ , and  $C_{max}$ , would be less than 200% with  $\geq 88\%$  probability, if the estimated GLSM ratio were 1.0. This is assuming a SD of no more than 0.463 on a natural logarithm scale, supported by previous Gilead study GS-US-402-1851. With 25% overage, a total sample size of 60 subjects (10 per group, 20 per cohort) will be required.

---

This study will be conducted in accordance with the guidelines of Good Clinical Practices (GCPs) including archiving of essential documents.

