### **1.3.1. Rationale for the Dose Selection**

This study will evaluate the impact of hepatic impairment on the single dose PK of 30 mg (Cohorts 1 and 2) and 10 mg (Cohort 3) GS-9674 administered under fed conditions (moderate fat breakfast based on results from food effect evaluations in study GS-US-402-1851). These doses were selected based on the observed PK of single- and multiple-dose administration of GS-9674 up to 300 mg in study GS-US-402-1851 in healthy subjects and on the preliminary data from Cohorts 1 and 2 of this study, which showed increased unbound exposure with degree of hepatic impairment. Based on the PK of GS-9674 across the range of doses evaluated, and GS-9674 exposure and PD response observed in study GS-US-402-1851, alterations of GS-9674 PK observed in this study as a result of hepatic impairment are expected to reflect the magnitude of alteration of steady-state GS-9674 pharmacokinetics in subjects with NASH.

Short-term safety data from clinical study GS-US-402-1851 and GS-US-402-2102 indicate that GS-9674 exposures higher than those expected in this study are well tolerated in healthy subjects with no clinically significant or treatment limiting adverse events or laboratory abnormalities.

This study will proceed in three sequential cohorts starting with mild (CPT Class A), then moderate (CPT Class B), followed by severe (CPT Class C) hepatic impairment with evaluation of preliminary safety and PK data from hepatic impaired subjects from each cohort prior to initiation of subsequent cohorts. In addition, the proposed 30 mg dose of GS-9674 in Cohorts 1 and 2 is 10-fold lower than the highest dose level previously evaluated (300 mg) in study GS-US-402-1851 which provided GS-9674 exposures 12- to 15- fold lower than those observed at the NOAEL in the 4-week repeat dose toxicity studies in the mouse and cynomolgous monkey (Section 1.2.21.2.2). Based on the preliminary exposures observed in Cohort 1 and 2 (Section 1.2.5.2) and expected further increases in unbound exposure in Cohort 3, the dose of GS-9674 is being reduced to 10 mg in subjects with severe hepatic impairment to cautiously maintain adequate exposure margins.

With the proposed doses, it is unlikely that plasma exposures of GS-9674 in hepatic impairment subjects would exceed previously observed exposures in healthy volunteers or exceed exposures observed at the NOAEL in the toxicity studies.

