If the upper bound of the 2-sided 90% CI of the GLSM ratio for  $AUC_{last}$ ,  $AUC_{inf}$ , and  $C_{max}$  is smaller than 2.0, we will reject the hypothesis that subjects with hepatic impairment exhibit average PK parameter (ie,  $AUC_{last}$ ,  $AUC_{inf}$ , and  $C_{max}$ ) increases of at least 100% for GS-9674 compared to subjects with normal hepatic function.

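### Is the ≥88% chance of an upper limit below 200% a misleading power statement for Cohort 3, given the ratios already seen in Cohorts 1 and 2?

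*Protocol*

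**What the plan says.** The sample-size paragraph is the same in substance in protocol 8.10, the synopsis and SAP 1.4. It covers all three cohorts: "For each cohort, with 16 (8 per group) evaluable subjects, the estimated upper limit of one-sided 95% CI of the GLSM ratio" of impaired to control subjects is to lie below 200% with at least 88% probability for AUClast, AUCinf and Cmax. The condition follows at once: "probability, if the estimated GLSM ratio were 1.0. This is assuming a SD of no more than 0.463 on a natural logarithm scale". The number per group is then raised from 8 to 10 by a 25% overage.

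The figure relates to the decision rule in protocol 8.7. If the upper bound of the 90% CI "is smaller than 2.0, the null hypothesis that subjects with mild, moderate or severe hepatic impairment exhibit average PK parameter increases of at least 100"% is rejected. SAP 8.3.2 repeats the rule: if the upper bound "is smaller than 2.0, we will reject the hypothesis that subjects with hepatic impairment exhibit average PK parameter" increases of that size.

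The current protocol also reports preliminary results from this study (Table 1-3) and bases the Cohort 3 dose rationale in section 1.3.1 partly "on the preliminary data from Cohorts 1 and 2 of this study, which showed increased unbound exposure with degree of hepatic impairment".

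**The concern.** Two features invite criticism.

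First, the paragraph assumes no effect of hepatic impairment, and the same protocol shows an effect. All six GS-9674 intervals in Table 1-3 exclude 1.0, and all six upper limits exceed 200% (229 to 367). The dose rationale was revised in light of these data, but the sample-size paragraph was not. A reader could take 88% as the realistic chance that severe impairment meets the 2.0 rule, and then read a miss as a well-powered negative result.

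Second, the condition is worded "if the estimated GLSM ratio were 1.0". A probability of this kind is normally stated for a true ratio, so the sentence may look wrong as well as out of date.

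The 88% is the only operating characteristic given for Cohort 3. If it misled, the reading of the severe-impairment comparison, and any dosing recommendation drawn from it, could suffer.

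**Working it through.** **Inputs.** n = 8 evaluable per group, log-scale SD 0.463 and ratio 1.0 (protocol 8.10). Limit 2.0, compared with the upper end of a two-sided 90% CI, which is one-sided 5% (protocol 8.7). The SD matches the single-dose 30 mg Cmax CV of 48.9% in Table 1-2: √ln(1 + 0.489²) = 0.463.

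**Step 1: reproduce the plan's figure.** SE = 0.463 × √(2/8) = 0.2315. Noncentrality = ln 2 / 0.2315 = 2.994. With 14 degrees of freedom and critical value t = 1.761, the noncentral t gives 88.5%. A simulation with separate group variances, as in the SAP model, gives 88.2%. The stated ≥88% reproduces. With all 10 per group evaluable it is 94.2%.

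**Step 2: the word *estimated*.** If the observed ratio were exactly 1.0, the upper limit is below 2.0 whenever the sample SD is below ln 2 / (1.761 × 0.5) = 0.787. The chance of that is P(χ²₁₄ < 14 × (0.787/0.463)²) = 99.98%. So 88% belongs to a true ratio of 1.0, but the literal reading also satisfies ≥88%.

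**Step 3: other true ratios.** Same formula, noncentrality = ln(2/ratio)/SE, SD 0.463, per parameter:

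| True ratio | Source | 8 per group | 10 per group |
|---|---|---|---|
| 1.00 | planning value | 88.5% | 94.2% |
| 1.25 | illustrative | 61% | 70% |
| 1.50 | illustrative | 32% | 38% |
| 1.57 | mild Cmax | 26% | 30% |
| 1.64 | moderate Cmax | 20% | 24% |
| 1.76 | mild AUCinf | 13% | 15% |
| 1.78 | mild AUClast | 12% | 14% |
| 2.30 | moderate AUCinf | 1.3% | 1.1% |
| 2.49 | moderate AUClast | 0.5% | 0.4% |

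A smaller SD does not alter the pattern. At 0.400 (the 10 mg Cmax CV of 41.6% in Table 1-2) the range with 8 per group is 31% down to 0.4%.

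**Step 4: all three parameters together.** The rule names three parameters and the 88% is per parameter. By simulation with 8 per group and true ratio 1.0, assuming an AUClast–AUCinf correlation of 0.99 and an AUC–Cmax correlation of 0.5 to 0.8:

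- SD 0.463 for all three: 80% to 83%.
- AUC SD 0.360 (30 mg AUCinf CV of 37.2%, Table 1-2; AUClast assumed equal) and Cmax SD 0.463: 87% to 88%.
- 10 mg values, AUC 0.296 (CV 30.3%) and Cmax 0.400: about 95%.

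Since 0.463 is stated as an upper bound and matches the Cmax value, the joint figure under the source study's own SDs is close to 88% or above it.

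**Step 5: precision.** The 90% CI runs from the ratio divided by, to the ratio multiplied by, exp(t × SE). That factor is exp(1.761 × 0.2315) = 1.50 with 8 per group and exp(1.734 × 0.2071) = 1.43 with 10. The factors observed in Table 1-3, √(upper/lower) at N = 10, are 1.39 to 1.47. The planned SD therefore predicts the width of these intervals well.

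**The case for a change.** The strongest case for a change is that one protocol holds two pictures of the drug. With a sample SD of 0.463, the largest observed ratio that can meet the rule is 2/1.50 = 1.33 (8 per group) or 2/1.43 = 1.40 (10 per group). Every GS-9674 ratio in Table 1-3 exceeds both. AUCinf rose from 1.76 in mild to 2.30 in moderate impairment, and nothing in the documents supports a ratio of 1.0 in severe impairment. Even at the lower 90% limits in Table 1-3 (1.08 to 1.69) the chance with 8 per group is 81% down to 17%, never 88%. The remedy would be a few sentences.

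The arithmetic stands, and so does the remark that the no-effect scenario was not borne out in Cohorts 1 and 2. Three links in the argument are weaker.

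- **No Cohort 3 ratio is given.** That cohort receives 10 mg, not 30 mg. Section 1.3.1 expects a rise in *unbound* exposure, whereas the 2.0 rule as planned is read on total AUC and Cmax. Cmax hardly moved between mild and moderate impairment (1.57 to 1.64). The range of 0.5% to 26% is a what-if, not a forecast.
- **The plan does not promise 88% unconditionally.** The assumed ratio and SD stand in the same passage. A sample-size section may record the basis on which N was chosen, and nothing in the documents requires it to be restated when preliminary data arrive.
- **The feared misreading is not in the plan.** Protocol 8.7 and SAP 8.3.2 say when the null hypothesis is rejected. Neither says that failing to reject it shows a twofold increase.

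**Conclusion.** The concern does not call for a change. The ≥88% is correct per parameter for a true ratio of 1.0 or below with a log SD of at most 0.463, and the paragraph states the ratio and SD it rests on. The slip between *estimated* and *true* is clerical and makes the statement false under neither reading (99.98% or 88.5%).

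If Cohort 3 total exposure behaved as in Cohorts 1 and 2, the per-parameter chance of meeting the rule would be 0.5% to 26% with 8 per group, or 0.4% to 30% with 10. That depends on carrying ratios across severity and dose, which the documents neither support nor exclude. It would make a miss likely, but it would not make the analysis wrong. The primary objective is to estimate exposure relative to matched controls. The ratio and its 90% CI are planned for each cohort, and their precision (a factor of about 1.43 to 1.50 either way) does not depend on the true ratio. A sensible reader will interpret severe impairment from that interval.

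Rewording would keep N, the model, the limit, the decision rule and every output, so it offers no gain in the result.
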